## 1. Introduction

This document summarizes the statistical methods to be implemented during the analysis of data for the post-approval study of the TECNIS® Toric IOL models ZCT450, ZCT525 and ZCT600. The purpose of this study is to evaluate the rate of severe visual distortion with these lenses in clinical practice. This study will be a prospective, multicenter, bilateral, open-label clinical investigation. Subjects are to be bilaterally implanted with at least one eye having a ZCT450, ZCT525 or ZCT600 IOL and the fellow eye having a high cylinder toric IOL (models ZCT300 to ZCT600).

The key timeframe for analysis will be the six month visit. The primary endpoint for this study is the rate of severe visual distortions defined as the proportion of subjects who report a severe visual distortion under overall circumstances at 6 months for any of the following 5 visual distortion items of interest:

- lines that slant, tilt, split or separate
- flat surfaces appearing curved
- objects appearing further away or closer than they actually are
- objects appearing to have a different size or shape
- physical discomfort related to vision

For the primary endpoint, severe visual distortions will be assessed using the overall circumstance reply at the 6 month visit. For the primary endpoint, the frequency and proportion of subjects reporting one or more of these items as severe will be used to determine the rate of severe visual distortions

Results from individual visual distortion items on the PRVDQ questionnaire will also be reported for the overall circumstance and the with and without correction circumstances.

Other endpoints include: refraction results, uncorrected and corrected distance visual acuity, medical/lens findings and adverse events.

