## 4. Postoperative Analyses – Key Endpoints

### 4.1 Visual Distortions – Primary Endpoint

The primary endpoint is the rate of severe visual distortions defined as the proportion of subjects who report a severe visual distortion under overall circumstances at 6 months for any of the 5 defined visual distortion items listed in section 1.0. The frequency and proportion of bilateral subjects with severe visual distortions will be reported along with the two-sided 95% confidence interval at the 6 month visit. Thus, the statistical focus is to estimate the rate of severe visual distortions.

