### 4.2 Other Visual Distortion Endpoints Related to Severe Visual Distortions

In addition to the above analysis related to the primary endpoint, other analyses will also be performed for severe visual distortion rates (based on the 5 defined items) in the overall circumstance and will include the frequency and proportion with severe visual distortions. Severe visual distortion data for the overall circumstance will be reported by the IOL group for bilateral subjects. The severe visual distortion rate will also be reported for all subjects enrolled in the study including bilateral subjects and those implanted in one eye (with a cataract, phakic condition or having another IOL (i.e. not a ZCT300-ZCT600 IOL) in the fellow eye). A trend analysis will be performed by plotting the severe visual distortion rate by increasing toric IOL cylinder power. To examine within subject changes for visual distortions (based on the 5 defined items in the overall circumstance) for subjects with data at both the 1 month and 6 month visits, the frequency and proportion will be reported for the following categories: those with severe distortions at both visits, those with severe distortions only at 1 month, those with severe distortions only at 6 months and those with no severe distortions at 1 month or 6 months. In addition, for subjects with severe visual distortions (based on the 5 defined items) at any time point, data will be provided indicating when the severe visual distortions were reported and the status at 6 months. Results for severe visual distortions will also be reported by investigational site. Any unusual patterns due to site will be noted (i.e. all severe visual distortions at 1 or 2 sites) and further analyses performed to address any site issues. Details on age, sex, race and cylinder will be reported for subjects experiencing severe visual distortions.

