To evaluate if IOL axis misalignment changes are associated with severe visual distortions, descriptive statistics for IOL axis misalignment will be reported for subjects with and without severe visual distortions. In this study, axis misalignment is defined as the difference between the Toric IOL axis marker location from the slit lamp evaluation and the steep meridian from the postoperative keratometry measurement. This measurement is intended to evaluate toric IOL misalignment as a possible reason for severe visual distortions experienced by a subject at a specific postoperative timepoint. This axis misalignment measurement is not a measure of toric IOL rotational stability, but a measure of toric IOL alignment relative to post-surgical keratometry steep meridian [as it is known that cataract surgery can induce changes in the cornea].

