### 4.3 Other Visual Distortion Endpoints:

The frequency and proportion with each response will also be reported for individual visual distortion items on the questionnaire for bilateral subjects for the overall circumstance and for the with and without correction circumstances.

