#### **7. Sample Size Calculations**

With 80 subjects and a severe visual distortion rate of 0.025, this study has 86% probability of achieving a half-width of 0.05 for a 95% confidence interval for the rate of severe visual distortions.

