**APPENDIX I**  
**TABLE LISTING**

	Primary Eyes	Fellow Eyes	All Subjects	Bilateral Subjects	Comments
ENROLLMENT/PREOP/OP					
Accountability/Enrollment					
No. of implants by IOL model by investigational site	x	x	x		
Accountability			x		
Demographics					
Demographic-age in years (N, Mean, SD, Min., Max), age in groups (<60,60-69,70-79,>=80), race, ethnicity, gender, iris color			x		
Operative Data					
Surgical complications: No. and percent with each response	x	x			
Surgical other procedures (No. and percent with each response)	x	x			
POSTOPERATIVE DATA					
Time frame for reporting: 6 Months					
Prescription offered at one month			x		
Primary Endpoint					
Primary endpoint – Overall severe visual distortions) No., percent and 95% CI for those with and without severe visual distortions at 6 Months				x	
Other Visual Distortion Analyses and Endpoints					
Overall severe visual distortions ( No, percent, for those with and without severe visual distortions			x	x	Also by IOL group for bilateral subjects
Overall severe visual distortions by site (No. and percent)				x	
Individual visual distortions-overall and with and without correction No, percent with each response for each item				x	
Listing of subjects with severe visual distortions including IOL group, age, race, gender, cylinder, SEQ, BCDVA, UCDVA.			x		
Plot of severe visual distortion rate by increasing IOL cylinder				x	
Axis Misalignment Analysis and Severe Visual Distortion					
Difference between IOL axis marker location and steep K meridian (N, mean, SD, median, min., max) for those with and without severe visual distortions	x	x			

	Primary Eyes	Fellow Eyes	All Subjects	Bilateral Subjects	Comments
Refraction Analyses					
Mean refractive data (Mean, S.D., median, min., max.):	x	x			For ZCT450-ZCT600 pooled and by IOL model
Percent reduction in cylinder					
Preop keratometric cylinder					
Postop refractive cylinder					For ZCT300-ZCT400 pooled
Difference btw. ref. cyl. and intended cyl.					
Spherical equivalent (SEQ)					
Difference btw. SEQ and intended SEQ					
Eyes within 0.5D and 1.0D of intended value (No., percent):	x	x			For ZCT450-ZCT600 pooled and by IOL model
Postop refractive cylinder					
Postop spherical equivalent					For ZCT300-ZCT400 pooled
Visual Acuity Analyses					
Monocular visual acuity by acuity line level (No., percent):	x	x			For ZCT450-ZCT600 pooled and by IOL model

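### SAP 4.2 relates misalignment and cylinder power only to a severe/not-severe flag with about 2 expected events; adding the item ratings already collected would give these analyses a better chance of being informative

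*SAP*

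**What the plan says.** SAP 4.2 states a purpose, "To evaluate if IOL axis misalignment changes are associated with severe visual distortions", and then a method: "descriptive statistics for IOL axis misalignment will be reported for subjects with and without severe visual distortions". The corresponding row of SAP Appendix I asks for "N, mean, SD, median, min., max) for those with and without severe visual distortions", for primary and fellow eyes. Protocol 20.4 uses the same split.

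For cylinder power, SAP 4.2 says: "A trend analysis will be performed by plotting the severe visual distortion rate by increasing toric IOL cylinder power". Appendix I lists this as a plot, and separately tabulates the severe rate by IOL group.

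The item ratings appear in SAP 4.3: "The frequency and proportion with each response will also be reported for individual visual distortion items on the questionnaire". In Appendix I that table is for bilateral subjects, with no split by lens group and no link to misalignment.

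Protocol 11.6 and Appendix A require the questionnaire, keratometry and the slit-lamp axis reading from every subject at 6 months. SAP 4.1 describes the statistical focus as estimating the severe rate. Section 7 sizes the study for that alone: "With 80 subjects and a severe visual distortion rate of 0.025, this study has 86% probability of achieving a half-width of 0.05".

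**The concern.** Misalignment of a high-cylinder lens is the mechanism the study was set up to watch. Protocol 2 raises spatial distortion from misalignment as a possibility, particularly for higher corrections. Protocol 18 says the risk may be greater with these models. SAP 4.2 sets itself the task of looking for that association, yet divides the sample into a group of about 2 and a group of about 78. The ratings of the other subjects, which may carry information on milder distortion, play no part.

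The practical risk is misreading. A table with no visible difference could be taken as reassurance when it carries almost no information. In the other direction, a plot built on one or two events can look like a gradient.

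**Working it through.** **Inputs.** N = 80 and severe rate 0.025 (SAP 7); up to 10% lost by 6 months, giving 72 (Protocol 11.8); at least 15 subjects with ZCT600 (Protocol 8); clinical hypothesis of a rate below 10% (Protocol 3). The documents set no test for these analyses, so every power figure below assumes a two-sided 5% test.

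**1. The plan's own figure.** The exact 95% interval half-width is 0.049 at 3/80 and 0.055 at 4/80, so a half-width of 0.05 needs at most 3 events. P(X ≤ 3 | 80, 0.025) = 0.859, which reproduces the stated 86%.

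**2. Size of the severe group.** Expected events = N × rate; probabilities are binomial.

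| N | Rate | Expected | P(0) | P(0 or 1) |
|---|---|---|---|---|
| 80 | 2.5% | 2.0 | 13% | 40% |
| 72 | 2.5% | 1.8 | 16% | 46% |
| 80 | 5% | 4.0 | 2% | 9% |
| 80 | 10% | 8.0 | <0.1% | 0.2% |

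With no event there is no severe group to describe. With one, its SD does not exist.

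**3. Misalignment difference needed.** For 80% power the difference in SD units is (1.96 + 0.84) × √(1/k + 1/(80 − k)), where k is the number of severe subjects.
- k = 2: 2.80 × √(0.500 + 0.0128) = 2.0 SD
- k = 4: 1.44 SD
- k = 8: 1.04 SD

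With k = 2, power is 10% for a difference of 0.5 SD and 29% for 1 SD.

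**4. Cylinder power.** If ZCT600 has its minimum of 15 subjects, expected events are 15 × 0.025 = 0.375, and the chance of none is 0.975^15 = 68%. The exact upper 95% limit for 0/15 is 1 − 0.025^(1/15) = 21.8%. As an illustration, one event in 15 (6.7%) and one in the other 65 (1.5%) would plot as roughly a four-fold rise resting on two people.

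**5. What the ratings could add.** The response scale is not in the documents. The simulation assumes four grades, 2.5% of subjects in the worst grade, and a bivariate normal model linking the size of misalignment to symptom severity, with 80 subjects. The share in the lowest grade was varied from 55% to 90% (splits from 55/25/17.5/2.5 to 90/5/2.5/2.5). Both analyses are rank-based.

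| Latent correlation | Severe flag | Four grades |
|---|---|---|
| 0.4 | about 20% | about 53% to 88% |
| 0.3 | about 13% | about 34% to 63% |

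At zero correlation, both reject in about 5% of runs or fewer.

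**6. Signed or absolute difference.** SAP 4.2 defines misalignment as a difference and does not say whether the sign is dropped. If severity depends on the size of misalignment (latent correlation 0.4), a rank correlation with the signed difference has only about 7% to 14% power. The gain in step 5 exists only for the absolute value.

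The corresponding gain for the cylinder analysis was not computed.

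**The case against.** The strongest reply is that the flag is the intended target. SAP 4.2 concerns severe distortion, its heading says so, and its analyses are descriptive with no test promised. With one or two severe subjects, the minimum and maximum in the Appendix I row show those subjects' actual misalignment beside the range of the others. That is a usable case description. All of this stands, and it is why the ratings analysis should be an exploratory addition and not a replacement.

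A reader might infer that the planned analyses cannot show an association. The documents do not support that. A difference of about 2 SD could show, and the severe count could be well above 2: the clinical hypothesis allows any rate below 10%, and SAP 2.1 counts a repositioned or explanted subject without a prior questionnaire as severe.

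A reader might also infer that the plan discards the ratings. It does not: SAP 4.3 tabulates them, and the general sentence in Protocol 20.2 on reporting by IOL group could cover a split by lens. What is missing is any planned link to misalignment, and any such split in the SAP's table list.

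It is also fair to say that the simulated gain is assumption-driven. A latent normal model carries the association evenly through the milder grades, which favours using them. Even then, at a correlation of 0.3 the ratings analysis falls short of 80% power, so it could not rule the mechanism out either.

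**Conclusion.** The point holds as an inexpensive improvement to two secondary analyses. At the planning rate, the severe-only comparisons rest on about 2 subjects, with a 40% chance of at most one, and have very little chance of showing or excluding an association unless the effect is very large or the rate is much higher. At a 5% rate the chance of at most one event falls to 9%, but about 1.4 SD is still needed for 80% power.

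The event counts follow directly from the plan's figures. The power gain for misalignment does not: it depends on an assumed four-grade scale, assumed distributions and assumed correlations, and on the inference from the documents' references to ratings, responses and severity that the answers are graded. The direction of the gain was the same for every distribution tried; its size is uncertain. The primary rate, its interval and the sample size are not in question.

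**What to change.** Keep the severe-only table, plot and listing. Add one table, labelled exploratory, to SAP 4.2 and Appendix I:

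- **Outcome.** For each bilateral subject, the worst overall-circumstance rating over the 5 items at 6 months. For repositioned or explanted subjects, use the pre-procedure questionnaire, following SAP 2.1. Assign the worst grade where SAP 2.1 deems the subject severe.
- **Misalignment.** Absolute difference between IOL axis and steep meridian, for an eye fixed in advance (for example the larger of the two eyes' values, or the primary eye). Use the pre-procedure axis measurement for repositioned or explanted subjects, so that they do not enter with a corrected axis. Report the Spearman correlation with a 95% CI.
- **Cylinder power.** Highest IOL cylinder per subject, with a Jonckheere-type ordinal trend test. A Cochran-Armitage test is for a binary outcome and would not use the ratings.
- **Interpretation.** State that the table addresses severity of distortion in general, not severe distortion alone, and that a null result does not exclude an association.

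The cost is one extra table with an unadjusted test, from data already collected. It needs no new visit, measurement or subject.

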### 4.3 Other Visual Distortion Endpoints:

The frequency and proportion with each response will also be reported for individual visual distortion items on the questionnaire for bilateral subjects for the overall circumstance and for the with and without correction circumstances.

### 4.4 Other Endpoints:

The mean percent reduction in cylinder will be reported for primary and fellow eyes at six months and will also be reported by IOL model. The percent reduction in cylinder is calculated for each eye using the following formula:.

$$100*((\text{Postop Ref. Cyl.} - \text{Preop K. Cyl.}) / (\text{Target Ref. Cyl.} - \text{Preop K. Cyl.}))$$

Key: Ref. Cyl.=absolute refractive cylinder; K. Cyl.=keratometric cylinder;

Refractive data will be referred to the corneal plane prior to determining percent reduction in cylinder.

To evaluate refractive predictability and refractive cylinder compared to intended, the mean absolute refractive cylinder, absolute refractive cylinder adjusted for the intended cylinder (i.e. target cylinder), spherical equivalent, and spherical equivalent adjusted for the intended spherical equivalent will be reported for primary and fellow eyes. The frequency and proportion of primary and fellow eyes within 0.5D and within 1.0D of intended values will be determined for refractive cylinder and spherical equivalent.

The frequency and proportion of primary and fellow eyes at each acuity line will be reported for monocular uncorrected and best corrected distance visual acuity at six months. Similar statistics will be reported for binocular visual acuity.

The frequency and proportion of medical and lens findings will also be reported for primary and fellow eyes. The frequency and proportion of adverse events at any time postoperative will also be reported for primary and fellow eyes for all subjects.

#### **5. One Month Prescription Data:**

The frequency and proportion of responses to the question related to offering of spectacle or contact prescription will be reported by IOL group at the one month visit.

#### **6. One Year Data:**

Visual distortion findings, adverse events and medical/lens findings at one year will be reported for subjects who experienced a repositioning procedure during the study or for subjects who were reported with severe visual distortions at the 6-month visit.

#### **7. Sample Size Calculations**

With 80 subjects and a severe visual distortion rate of 0.025, this study has 86% probability of achieving a half-width of 0.05 for a 95% confidence interval for the rate of severe visual distortions.

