**STUDY POPULATION CHARACTERISTICS:**

Condition:	Bilateral cataracts with corneal astigmatism of approximately 2.00 D to 4.75 D (with 3.00 D to 4.75 D in at least one eye) based on the combination of preoperative keratometric cylinder and the expected effect of surgically-induced astigmatism (SIA).
Number of Subjects:	Up to 120 subjects will be enrolled to achieve bilateral implantation in approximately 80 subjects; a minimum of 15 subjects will be implanted with a TECNIS Toric ZCT600 in at least one eye, and the remaining subjects will be implanted with either a TECNIS Toric ZCT450, ZCT525 or ZCT600 in at least one eye.
	This is a bilateral study; both eyes must be implanted with a TECNIS Toric IOL (ZCT300 – ZCT600); however, each eye may have a different TECNIS Toric IOL implanted as determined by the surgeon however as stated above, at least one eye must be implanted with a TECNIS Toric ECR IOL (ZCT450-ZCT600). The eye with the highest toric power IOL will determine the model group.
	Each site should enroll approximately 6 subjects and no site may enroll more than 20% of the enrollment total.

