## **8. STUDY POPULATION**

All subjects will be enrolled from the normal surgical cataract population at up to 20 sites in the U.S.A. This study will include only subjects intended to undergo bilateral primary phacoemulsification cataract extraction and IOL implantation who have approximately 3.00 D to 4.75 D of corneal astigmatism in at least one eye requiring correction based on the combination of preoperative keratometric cylinder and the expected effect of SIA. Up to 120 subjects will be enrolled to achieve approximately 80 bilaterally implanted subjects. A minimum of 15 subjects will be implanted with the TECNIS Toric ZCT600 in at least one eye; the remaining subjects are to be implanted with the TECNIS Toric ZCT450, ZCT525 or ZCT600 in at least one eye. The eye with the highest toric power will define the toric group. Both eyes will be implanted with a high cylinder TECNIS Toric IOL (Models ZCT300-ZCT600), but the fellow eye may have a lower cylinder correction toric IOL implanted (i.e. ZCT300, ZCT375 and ZCT400). Each site should enroll approximately 6 subjects, and no site may enroll more than 20% of the enrollment total.

This study will include only subjects who meet all of the study inclusion and exclusion criteria in both eyes. All subjects who meet the inclusion/exclusion criteria will be offered enrollment in the study. Eligibility criteria may not be waived by the investigator. Any questions regarding patient eligibility are to be discussed with AMO prior to subject enrollment.

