## **11.6 POSTOPERATIVE PROCEDURES**

Postoperatively, subjects will be examined according to the schedule in Section 11.2, Visit Schedule. All subjects will be examined at the 1- and 6-month study visits. If a subject requires a lens repositioning procedure due to IOL misalignment or if a subject reports a severe visual distortion at 6 months, the subject will also undergo a final visit at 1 year.

At the 1-month visit, a spectacle and/or contact lens prescription will be offered to each subject. Postoperative procedures will include uncorrected and best corrected visual acuities, manifest refraction, intraocular pressure and biomicroscopic slit-lamp examination. In addition, if the subject has a spontaneous report of any of the 5 visual distortion items of interest or of blurred or hazy vision, the questionnaire will be administered and keratometry and toric IOL axis measurements will be performed.

Primary 6-month postoperative data collection consists of administration of a subject questionnaire for determination of visual distortion reports, manifest refraction, distance visual acuities, intraocular pressure, keratometry, and a biomicroscopic slit-lamp exam for determination of toric IOL axis position and for any adverse events.

If outside of a scheduled study visit, a subject has a spontaneous report of; 1) any of the 5 visual distortion items of interest or 2) blurred or hazy vision at one month postoperatively or later, the PRVDQ questionnaire will be administered and keratometry and toric IOL axis measurements will be performed. Exam details will be documented on an unscheduled visit form.

If a subject reports a severe visual distortion or has experienced a serious or device-related adverse event at any unscheduled study visit, uncorrected distance visual acuity, best corrected distance visual acuity, manifest refraction, keratometry, intraocular pressure and biomicroscopic slit-lam examinations will be performed.

Subjects should be assessed at each visit for occurrence of and/or change in status of any adverse events, particularly serious and/or device-related adverse events. If a serious or device-related adverse event occurs, details of the event are to be captured on an adverse event CRF and the exam details are to be captured on the appropriate visit CRF (i.e., 1-month, 6-month, 1-year or unscheduled). The event will be followed up as necessary and details captured on adverse event follow-up CRFs until resolution.

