#### SUBJECT FOLLOW-UP

To minimize subjects lost to follow-up, subjects will be provided compensation for their time and participation in the study at the 1- and 6-month postoperative exams.

Additionally, sites will be compensated for completion of the 1- and 6-month exams and will be provided frequent listings of upcoming 1- and 6-month subject examinations as well as follow-up reminder cards to send to the subjects. It is anticipated that at least 90% of subjects will be available for the 6-month study visit (i.e., no more than a 10% lost-to-follow-up rate at 6 months postoperatively). If a subject has a confirmed report of severe visual distortion(s) per the questionnaire, prior to the 6-month exam, every effort is to be made to ensure that subject returns for the 6-month exam. The investigative site shall make a minimum of at least three attempts (phone calls/emails and/or letters) to locate missing subjects.

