### 20.2 ANALYSIS POPULATION

For the primary endpoint and most visual distortion endpoints, the primary analysis population will be all bilaterally implanted subjects having available data at the 6-month visit. Data will also be reported for all subjects including bilateral subjects and those with only one eye implanted (having a phakic lens, a cataract or other IOL in the fellow eye). Data will also be reported by IOL group. If a subject does not have overall severe visual distortion data available at the 6-month visit (or had a repositioning procedure or IOL removal performed) then data for this endpoint will be carried forward from the most recent visit (for general missing data) or the visit with data taken prior to the IOL

repositioning or removal. If a subject had an IOL repositioning/removal and no questionnaire data prior to the procedure, then the subject will be considered to have had a severe visual distortion for this endpoint. An additional analysis will be performed for the primary endpoint using multiple imputation techniques for those with no questionnaire data available. Sensitivity analyses such as worst-case and best-case will also be performed.

Refraction, visual acuity, medical/lens findings, axis evaluation and adverse events will be reported for primary eyes (those having the higher cylinder IOL or the first eye implanted if the same IOL is implanted in both eyes) and fellow eyes. Data will be reported separately for ZCT450-ZCT600 eyes and ZCT 300-ZCT400 eyes.

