## 20.6 SAMPLE SIZE CALCULATIONS

With 80 subjects and a rate of 0.025 for severe visual distortions, this study has 86% probability of achieving a half-width of 0.05 for a 95% confidence interval for the rate of severe visual distortions.

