## 2. Analysis Populations and Data Conventions

### 2.1 Analysis Population

The primary analysis population will be all bilaterally implanted subjects having available data at the six month visit. In addition, data for severe visual distortions (based on the 5 defined items) will also be reported for all subjects including bilateral subjects and those with only one eye implanted and the fellow eye having phakic status, a cataract, or another IOL. If a subject does not have overall severe visual distortion data available at the six month visit (or had a repositioning procedure or IOL removal performed) then data for the endpoint will be carried forward from the most recent postoperative visit (for general missing data) or the postoperative visit prior to the IOL repositioning or removal. If a subject had an IOL repositioning/removal procedure and did not have visual distortion data available prior to the procedure, then the subject will be considered to have had severe visual distortions for the primary endpoint. For overall severe visual distortions based on the 5 defined items, an additional analysis population will be evaluated that includes all subjects with last observation carried forward for missing data as described above as well as use of data imputation for subjects with no available questionnaire data at any time point. Imputation for those with no questionnaire data will be performed using multiple imputation techniques as described in Little and Rubin and implemented using the MI and MIANALYZE procedures in SAS® (Version 9.2 or later

version if available). Additional sensitivity analyses will be performed including worst-case analysis where all missing visual distortion data (using the 5 defined items) will be treated as having a severe visual distortion and best-case analysis where missing data is treated as having no severe visual distortion. If more than 10 percent of visual distortion data (using the 5 defined items) are missing then a tipping point analysis will also be evaluated.

Data will typically be reported for all bilateral subjects, however, for some analyses, such as the overall visual distortion endpoint, data will also be reported by IOL group. Subjects who have a lower cylinder IOL in one eye (e.g. ZCT300) and a higher cylinder IOL in the fellow eye (e.g. ZCT450) will be placed in the higher cylinder group for analysis when reporting data by subject.

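### The 86% precision figure is correct for 80 evaluable subjects but makes no allowance for the 10% loss the protocol anticipates; at 72 evaluable it is 73%, though the expected interval hardly widens

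*SAP*

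**What the plan says.** - **Precision statement.** SAP 7: "With 80 subjects and a severe visual distortion rate of 0.025, this study has 86% probability of achieving a half-width of 0.05". Protocol 20.6 gives the same figures: "this study has 86% probability of achieving a half-width of 0.05 for a 95% confidence interval". Neither names the interval method. SAP 4.1 and Protocol 20.3 specify only a two-sided 95% interval.
- **What 80 is elsewhere.** Protocol Synopsis, Number of Subjects: "Up to 120 subjects will be enrolled to achieve bilateral implantation in approximately 80 subjects". Protocol 8 agrees: "Up to 120 subjects will be enrolled to achieve approximately 80 bilaterally implanted subjects".
- **Who is analysed.** SAP 2.1: "The primary analysis population will be all bilaterally implanted subjects having available data at the six month visit". Protocol 20.2 defines the same population.
- **Anticipated loss.** Protocol 11.8, Subject Follow-up, expects that "at least 90% of subjects will be available for the 6-month study visit (i.e., no more than a 10% lost-to-follow-up rate".
- **Carry-forward.** SAP 2.1 fills a missing 6-month value from the latest postoperative visit. Protocol 20.2 has the same rule without the word postoperative. Both documents count a repositioned or explanted subject with no earlier questionnaire as severe.
- **When the questionnaire is given.** Appendix A requires it preoperatively and at 6 months. At 1 month, Protocol 11.6 requires it only "if the subject has a spontaneous report of any of the 5 visual distortion items of interest or of blurred or hazy vision". Appendix A applies a similar condition to unscheduled visits and adds the case of a pending repositioning.

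**The concern.** The precision statement is the only quantitative justification of the study size. It uses as its denominator the number the study aims to implant, while the primary analysis uses those implanted subjects who also have data at 6 months. The protocol itself allows for up to a tenth of subjects being unavailable at that visit. The ceiling of 120 enrolled does not cover this, because the text ties it to reaching about 80 implanted, not to replacing later losses.

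Carry-forward could in principle close the gap. Under the SAP it mostly does not, because a subject who made no spontaneous complaint and had no repositioning has no postoperative questionnaire to carry forward. Such subjects enter only the imputation and sensitivity analyses.

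At stake is whether the stated precision is what the design delivers at its own limit for loss. No decision rule depends on the 86%.

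**Working it through.** **Inputs**

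- True rate 0.025, target half-width 0.05, N = 80: SAP 7 and Protocol 20.6.
- Two-sided 95% interval: SAP 4.1 and Protocol 20.3.
- Lowest anticipated evaluable number: 0.90 × 80 = 72, from Protocol 11.8 and the implant target.
- Interval method: not stated, so several were tried.

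**Formulas**

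For x events in n subjects, half-width h(x, n) = (upper limit − lower limit)/2. Let k be the largest x with h(x, n) ≤ 0.05.

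- Probability of meeting the target: P(X ≤ k), with X ~ Binomial(n, 0.025).
- Expected half-width: the sum over x of P(X = x) × h(x, n).

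**Step 1. Reproduce the plan's figure at n = 80**

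| Method | h at 3 events | h at 4 events | k | P(X ≤ k) |
|---|---|---|---|---|
| Clopper-Pearson | 0.0490 | 0.0547 | 3 | 85.9% |
| Wilson | 0.0459 | 0.0510 | 3 | 85.9% |
| Wald, continuity-corrected | 0.0479 | 0.0540 | 3 | 85.9% |
| Wald | 0.0416 | 0.0478 | 4 | 95.0% |
| Jeffreys | 0.0430 | 0.0487 | 4 | 95.0% |
| Agresti-Coull | 0.0503 | 0.0548 | 2 | 67.7% |

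The stated 86% is P(X ≤ 3 | 80, 0.025) = 0.8594. Three methods give it, so the figure does not by itself identify the interval. Plain Wald does not give it.

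**Step 2. Repeat at n = 72**

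At 2 events h is 0.0467 (Clopper-Pearson) or 0.0440 (Wilson). At 3 events it is 0.0541 or 0.0506. Hence k = 2 for both, and P(X ≤ 2 | 72, 0.025) = 0.7313, or 73.1%. Continuity-corrected Wald, without truncation at zero, also gives 73.1% (h at 3 events 0.0531).

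**Step 3. Values between 72 and 80**

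| Evaluable n | Clopper-Pearson | Wilson |
|---|---|---|
| 72 | 73.1% | 73.1% |
| 73 | 72.5% | 89.0% |
| 78 | 69.0% | 86.8% |
| 79 | 86.4% | 86.4% |
| 80 | 85.9% | 85.9% |

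The probability is a step function of n. With Clopper-Pearson, h at 3 events is 0.0495 at n = 79 and 0.0502 at n = 78, so a change of 0.0007 moves the probability by 17 points. From 78 down to 72 it then rises from 69.0% to 73.1%. With Wilson it rises from 85.9% to 89.0% as n falls from 80 to 73, and drops only at 72.

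**Step 4. Expected half-width**

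| Method | n = 80 | n = 72 | Change |
|---|---|---|---|
| Clopper-Pearson | 0.0406 | 0.0433 | 0.0027 |
| Wilson | 0.0386 | 0.0412 | 0.0026 |

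**Step 5. Would more subjects help?**

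Implanting 88 and losing 10% leaves 79 (0.9 × 88 = 79.2). Going from 72 to 79 evaluable narrows the expected half-width by 0.0433 − 0.0409 = 0.0024 (Clopper-Pearson) or 0.0412 − 0.0389 = 0.0023 (Wilson), about 0.002 in each case.

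**The case against.** **The figure is correct as written.** This stands. Both documents say only 80 subjects; that these are the implanted subjects, with no allowance for loss, is an inference from the implant target. It is a reasonable one, since no other group of 80 appears in the plan, but 80 is approximate and 72 is a floor, not a forecast.

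**Under the protocol's own wording, N = 80 may be right.** This stands in part. Protocol 20.2 carries forward from the most recent visit, and every subject completes a questionnaire preoperatively. Read literally, almost every implanted subject has a value. The range of 72 to 80 is therefore the SAP reading. This is a reason to reconcile the two sentences, because they determine who is evaluable. Counting repositioned or explanted subjects as severe also keeps a few in the analysis.

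**The fall in probability is largely an artefact.** This stands. A reader might infer from the 69.0% at 78 that dropout steadily erodes precision. Step 3 shows otherwise: 72 does better than 78 with Clopper-Pearson, and Wilson holds 86–89% from 73 to 80.

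**Two stronger readings do not hold.** A reader might infer that the 86% cannot be matched to the planned analysis. It can: it matches Clopper-Pearson or Wilson at 80. A reader might also fear a zero-width interval if no events occur. That happens only with plain Wald, which gives 95.0% rather than 86%, and nothing in the documents suggests Wald is planned.

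**Little depends on it.** This also stands. SAP 4.1 describes the aim as estimation. Even set beside the 10% clinical hypothesis, the largest count with an exact upper limit below 10% is 2 at both sizes (8.7% for 2/80, 9.7% for 2/72; three events give 10.6% and 11.7%).

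**Conclusion.** The point holds as a minor one. The 86% is right for 80 evaluable subjects, but it is not what the design delivers at the protocol's own limit for loss. With 72 evaluable the probability is 73.1% under Clopper-Pearson or Wilson. The practical loss of precision is an expected half-width of 0.043 rather than 0.041 (Clopper-Pearson), or 0.041 rather than 0.039 (Wilson).

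This rests on four assumptions: about 80 are implanted; loss reaches the full 10%; carry-forward follows the SAP and restores few of the missing; and the interval is one that reproduces 86% at 80. The documents do not support a conclusion that the study is too small or that its primary estimate would be unreliable.

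**What to change.** 1. In SAP 7 and Protocol 20.6, name the interval (Clopper-Pearson or Wilson) and specify the same one in SAP 4.1 and Protocol 20.3. Both reproduce 86% and keep coverage at n = 80 and a true rate of 0.025 (98.5% and 95.0%). Continuity-corrected Wald also reproduces 86% but covers only 86.7%.
2. Restate the precision sentence in both places, for example:

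   > With 80 evaluable subjects and a true rate of 0.025, the probability of a half-width of 0.05 or less is 86%; with 72 evaluable (10% loss) it is 73%. The expected half-width is 0.041 and 0.043 respectively (Clopper-Pearson) [or 0.039 and 0.041 (Wilson)].

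3. Add the word postoperative to the carry-forward sentence in Protocol 20.2 so that it matches SAP 2.1.

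**Cost.** Wording only. Added enrolment is not warranted: 88 implanted would fit under the ceiling of 120 but gain only about 0.002 in expected half-width. The downsides are a less favourable stated figure and, if Clopper-Pearson is chosen, a slightly wider interval (0.049 against 0.046 with Wilson at 3 events in 80).
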